# 9) CCI

<Investigation point>

To be performed once each in the period from Week 4/ Day 22 to Week 6/ Day 36 and the period from Week 49/ Day 337 to Week 51/ Day 351.

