## 11) Muscle biopsy

<Investigation point>

To be performed once in the period from Week 49/ Day 337 to Week 51/ Day 351. To be performed after MRI or CT, motor function assessment, respiratory function assessment, cardiac function assessment, and quantitative muscle strength assessment.

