# 6.5.3 For Withdrawal in the Period from Week 1/ Day 1 to Week 49/ Day 337 of Part 2-Extension or from Week 1/ Day 1 to Week 49/ Day 337 of Part 2-Extension-2

- 1) Investigating concomitant medications and concomitant therapy
- 2) Investigating adverse events
- 3) Height and body weight
- 4) Vital signs and clinical findings
- 5) Blood tests
- 6) Urinalysis

- 7) 12-lead electrocardiogram
- 8) CCI \*15
- 9) MRI or CT

<Location of imaging>

Upper arm: MRI or CT (to confirm the location of muscle biopsy)

Thigh: MRI

- 10) Muscle biopsy
- 11) Motor function assessment (lower limbs and upper limbs)\*16
- 12) Respiratory function assessment
- 13) Cardiac function assessment
- 14) Quantitative muscle strength assessment
- 15) Blood collection
  - Pharmacokinetics
  - Anti-dystrophin antibody
  - Anti-DS-5141b antibody
- 16) Urine collection
  - Urine protein
- \*15: To be performed if the subject is withdrawn in the period from Week 1/ Day 1 to Week 49/ Day 337 of Part 2-Extension-2.
- \*16: Not necessary if motor function assessment (upper limbs) was not performed even once in the period from Week 24/ Day 168 to Week 37/ Day 253 (pre-dose) of Part 2-Extension-2.
- 6.5.4 For Withdrawal in the Period from Day 16 to Day 64 of Part 1, from Day 86 to Day 162 of Part 2, from Week 49/ Day 338 to Week 52/ Day 358 of Part 2-Extension, or from Week 49/ Day 338 to Week 52/ Day 358 of Part 2-Extension-2
- 1) Investigating concomitant medications and concomitant therapy
- 2) Investigating adverse events
- 3) Height and body weight
- 4) Vital signs and clinical findings
- 5) Blood tests and urinalysis
- 6) 12-lead electrocardiogram
- 7) (CC) \*17

8) MRI or  $CT^{*18}$ 

<Location of imaging>

Upper arm: MRI or CT (to confirm the location of muscle biopsy)

Thigh: MRI

- 9) Muscle biopsy\*18
- 10) Motor function assessment (lower limbs and upper limbs)\*18, 19
- 11) Respiratory function assessment\*18
- 12) Cardiac function assessment\*18
- 13) Quantitative muscle strength assessment\*18
- \*17: To be performed for subjects who participated in Part 2-Extension-2, but not necessary if performed on Week 49/ Day 337 of Part 2-Extension-2 in subjects withdrawn in the period from Week 49/ Day 338 to Week 52/ Day 358 of Part 2-Extension-2.

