- \*18: Not necessary in subjects withdrawn in the period from Day 86 to Day 162 of Part 2 if performed on Day 85 of Part 2. Not necessary for subjects withdrawn in the period from Week 49/ Day 338 to Week 52/ Day 358 of Part 2-Extension if performed on Week 49/ Day 337 of Part 2-Extension, and not necessary for subjects withdrawn in the period from Week 49/ Day 338 to Week 52/ Day 358 of Part 2-Extension-2 if performed on Week 49/ Day 337 of Part 2-Extension-2.
- \*19: Not necessary if motor function assessment (upper limbs) was not performed even once in the period from Week 24/ Day 168 to Week 37/ Day 253 (pre-dose) of Part 2-Extension-2.

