# 6.9 Expression of Dystrophin Protein and Production of Exon 45-Skipped Dystrophin mRNA in Muscle Tissue (Muscle Biopsy)

To measure the dystrophin protein in muscle tissue and the dystrophin mRNA induced by exon 45 skipping, after registration, before the first dose of the study drug in each subject, after the last dose of the study drug (Day 85 to Day 99, or at withdrawal) in Part 2, after the last dose of the study drug (Week 49/ Day 337 to Week 51/ Day 351, or at withdrawal) in Part 2-Extension, and after the last dose of the study drug (Week 49/ Day 337 to Week 51/ Day 351, or at withdrawal) in Part 2-Extension-2, muscle tissue will be collected from, in principle, the biceps brachii muscle by open muscle biopsy. The location of collection will be decided after checking the condition of the muscle by MRI or CT performed in advance. After collection, the

specimen will be processed promptly, and stored frozen (set temperature:  $\leq -70^{\circ}$ C) in a container prepared by the sponsor or central laboratory until it is submitted to the clinical specimen storage facility contracted by the sponsor. Details are specified in a separate procedure.

The investigator or subinvestigator will record whether a muscle biopsy was performed, the date of biopsy, and the region of the collected muscle on the case report form.

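### Part 2-Extension-2: the waiver of a repeat biopsy at withdrawal names Day 337 only, although the biopsy may be done up to Day 351 (drafting error, low severity)

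*Combined protocol and SAP*

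**What the plan says.** **Scheduled tests.** Section 6.4.5.2, item 11, says of the muscle biopsy: "To be performed once in the period from Week 49/ Day 337 to Week 51/ Day 351". It also fixes the order: "To be performed after MRI or CT, motor function assessment, respiratory function assessment, cardiac function assessment", and muscle strength as well. Items 10 and 12 to 16 (imaging, motor, respiratory, cardiac and strength tests) have the same post-treatment window. So does the redacted test in item 9, whose second occasion is given as "and the period from Week 49/ Day 337 to Week 51/ Day 351". Section 6.9 describes the biopsy as open and times it "after the last dose of the study drug (Week 49/ Day 337 to Week 51/ Day 351, or at withdrawal) in Part 2-Extension-2".

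**Withdrawal tests.** The heading of 6.5.3 covers withdrawal "or from Week 1/ Day 1 to Week 49/ Day 337 of Part 2-Extension-2", and that of 6.5.4 covers withdrawal "or from Week 49/ Day 338 to Week 52/ Day 358 of Part 2-Extension-2". The 6.5.4 list includes the redacted test (footnote *17) and imaging, biopsy, motor, respiratory, cardiac and strength tests (footnote *18). Under 6.5 they are due within 7 days of the decision to withdraw the subject, where feasible.

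**The waiver.** Footnote *17 calls the redacted test "not necessary if performed on Week 49/ Day 337 of Part 2-Extension-2 in subjects withdrawn in the period from Week 49/ Day 338" onward. Footnote *18 ends with the matching clause for the other items: withdrawals up to "Week 52/ Day 358 of Part 2-Extension-2 if performed on Week 49/ Day 337 of Part 2-Extension-2".

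**The concern.** The schedule gives a 15-day window, while the waiver names its first day. A boy who has had his biopsy on time, but after Day 337, meets the condition for being listed again and does not meet the condition for being excused. No other waiver for tests done on Day 338 to Day 351 appears in the visible text.

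At stake is an avoidable open biopsy in a child, together with repeat imaging and function tests. Nothing planned would use the result: section 11.4.2.1 lists dystrophin after the last dose of Part 2-Extension-2 and makes no provision for a second value from the same part. Repeat function tests would also sit badly with the plan's own practice. At baseline, footnotes *6 and *7 of section 6.4.1 require these tests to be at least 28 days after a biopsy.

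**Working it through.** The plan gives no figure to reproduce. The check compares the clauses and counts days.

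**Inputs**
- Biopsy and test window: Day 337 to Day 351 (6.4.5.2, 6.9).
- Withdrawal period: Day 338 to Day 358 (6.5.4 heading).
- Waiver day: Day 337 (footnotes *17 and *18).
- Deadline for withdrawal tests: 7 days (6.5).
- Visit window: ±2 days for items from Day 8 to Day 344 (6.4.5.2).
- Last dose: Day 330 (6.7, 48th dose).

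**How much of the window is covered**
- Permitted days: 351 − 337 + 1 = 15.
- Literal reading: 1 day covered, 15 − 1 = 14 uncovered (Day 338 to Day 351).
- Visit reading with ±2 days: Day 335 to Day 339, of which Day 337 to Day 339 lie in the permitted window. That covers 3 days and leaves 15 − 3 = 12 uncovered (Day 340 to Day 351).

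**Is a biopsy on Day 337 the usual case?** Probably not. It must follow imaging and all function tests, and items 12, 13 and 16 of 6.4.5.2 require the motor and strength tests twice in this window. An uncovered day is the likelier one.

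**Worked example**
- Biopsy on Day 345, withdrawal on Day 350.
- 338 ≤ 350 ≤ 358, so 6.5.4 applies. Day 345 is not Day 337 and lies outside Day 337 to Day 339, so neither reading excuses the repeat.
- Tests are due by 350 + 7 = Day 357, at most 357 − 345 = 12 days after the first biopsy.

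**Withdrawal days that trigger a repeat**, counted from the biopsy day to Day 358
- Biopsy on Day 345: 358 − 345 + 1 = 14 days.
- Biopsy on Day 351: 358 − 351 + 1 = 8 days.

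These are calendar opportunities, not probabilities.

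**Timing of a repeat.** The scheduled biopsy falls 337 − 330 = 7 to 351 − 330 = 21 days after the last dose. The latest repeat, after withdrawal on Day 358 and the 7-day allowance, is Day 365, or 365 − 330 = 35 days after it.

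**The case against.** The strongest reply is that Day 337 is a visit label for the whole post-treatment round.
- In the follow-up period, vital signs, blood tests, urinalysis and ECG are scheduled only at Day 337 and Day 358, and the 15-day window opens at the first of these.
- The shorthand recurs: the Part 2 clause of footnote *18 names Day 85 where the tests run from Day 85 to Day 99.
- The literal reading leaves the biopsy waiver almost empty, which is a reason to doubt that it was meant.
- Appendix 3, the timing table, might settle the matter but is not reproduced in the text available.

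This reading may well be what the authors intended. It is not stated, however, and even a ±2-day visit window leaves 12 days uncovered. Elsewhere the plan writes Day 337 alone for single-visit items such as the antibody samples, and the full range for the biopsy and function tests. The boundary between 6.5.3 and 6.5.4 also uses Day 337 and Day 338 as calendar days, although it fits either reading. Footnote *19 writes out a range, but that is weak evidence, because its range spans two separate assessment rounds that no single visit label could express.

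The second reply is that the duty is soft. That stands as a limit on harm. Section 6.5 asks for the tests only where feasible, section 4.3 makes them depend on the family's cooperation, and section 6.1 ends the study duration early for a boy who has difficulty continuing, for example one who cannot attend. None of these says that a feasible repeat is unnecessary.

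The third reply is that hardly anyone is exposed. This also stands. A boy must complete dosing, have his biopsy, not enter the long-term study, and then be formally withdrawn with little left except the Day 358 visit. Six boys are planned (11.7), and no withdrawal rate is given.

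**Conclusion.** The rule is wrong as written, and the severity is low. The footnotes excuse a repeat on 1 of 15 permitted days read literally, or 3 of 15 with a ±2-day visit window. The conclusion rests on the visible text and could soften if Appendix 3 shows Day 337 as a column covering the whole window.

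Three stronger readings are tempting, and the documents do not support them.
- A reader might infer that the protocol intends or compels a second biopsy. The scheduled biopsy is to be done once in its window, and 6.9 offers withdrawal as an alternative time, so one biopsy was intended. The withdrawal list is also not absolute.
- A reader might infer harm to the primary endpoint. The analysis is descriptive, without hypothesis tests (11.1), and no planned analysis, power or error rate changes.
- A reader might lengthen the exposure by applying the ±7-day window to Day 358. That window belongs to items performed at that visit, whereas the 6.5.4 heading fixes the withdrawal period at Day 338 to Day 358.

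The matching wording for Part 2 and Part 2-Extension no longer matters: section 1.2.6 reports Part 2 complete and Part 2-Extension discontinued, with Part 2-Extension-2 in progress.

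**What to change.** In the Part 2-Extension-2 clauses of footnotes *17 and *18, replace the condition that the item was done on Day 337 with the condition that it has already been done after the last dose of study drug, and give Week 49/ Day 337 to Week 51/ Day 351 in brackets as the scheduled window. Tying the waiver to the last dose also excuses a biopsy done slightly outside the window.

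Uncovered days then fall from 14 of 15 (or 12 of 15) to 0 of 15. A boy who withdraws before his biopsy is still listed for it, as now. The clauses for Part 2 and Part 2-Extension can stay as they are.

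The cost is one phrase in each of two footnotes. No data are lost and no analysis changes.

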#### 6.6 Follow-up After Withdrawal from the Study

At 28 days after the last dose of the study drug (acceptable limit:  $\pm 7$  days), the following investigations, examinations, and tests will be performed, as far as possible. The contents of the tests will be the same as those during the study period.

- 1) Investigating concomitant medications and concomitant therapy
- 2) Investigating adverse events
- 3) Vital signs and clinical findings
- 4) Blood tests and urinalysis
- 5) 12-lead electrocardiogram

#### 6.7 Pharmacokinetics (Blood Collection [Plasma])

At the time of blood collection for pharmacokinetics, 1 mL of blood will be collected in a blood collection tube prepared by the sponsor or central laboratory. After collection, the blood will be promptly mixed by inversion mixing. The plasma obtained by centrifugal separation will be stored frozen (set temperature:  $\leq -70^{\circ}$ C) until it is submitted to the clinical specimen storage facility contracted by the sponsor. Details are specified in a separate procedure.

The investigator or subinvestigator will record whether blood was collected and the date/time of blood collection on the case report form.

<Blood collection point>

• Part 1 (each dose level)

First dose:

Day 1 (pre-dose and 0.5 hours, 1 hour, 2 hours, 4 hours, 6 hours, and 8 hours post-dose), Day 2 (24 hours post-dose), Day 4 (72 hours post-dose)

Second dose:

Day 8 (pre-dose), Day 9 (24 hours post-dose), Day 11 (72 hours post-dose), Day 15 (7 days post-dose), Day 36 (4 weeks post-dose), Day 64 (8 weeks post-dose)

Part 2

First dose:

Day 1 (pre-dose and 0.5 hours, 1 hour, 2 hours, 4 hours, 6 hours, and 8 hours post-dose), Day 2 (24 hours post-dose)

Second dose, fourth dose, sixth dose, eighth dose, 10th dose:

Day 8 (pre-dose), Day 22 (pre-dose), Day 36 (pre-dose), Day 50 (pre-dose), Day 64 (pre-dose)

12th dose:

Day 78 (pre-dose, 0.5 hours, 1 hour, 2 hours, 4 hours, 6 hours, and 8 hours post-dose), Day 79 (24 hours post-dose), Day 85 (7 days post-dose), Day 106 (4 weeks post-dose), Day 134 (8 weeks post-dose), Day 162 (12 weeks post-dose)

 Part 2-Extension and Part 2-Extension-2 (subjects continuing participation from Part 2 and Part 2-Extension)

First dose:

Week 1/ Day 1 (pre-dose and 4 hours post-dose), Week 1/ Day 2 (24 hours post-dose)

Second dose:

Week 2/Day 8 (pre-dose)

Fifth dose, ninth dose, 13th dose, 17th dose, 21st dose, 25th dose, 29th dose, 33rd dose, 37th dose, 41st dose, 45th dose:

Week 5/ Day 29 (pre-dose), Week 9/ Day 57 (pre-dose), Week 13/ Day 85 (pre-dose), Week 17/ Day 113 (pre-dose), Week 21/ Day 141 (pre-dose), Week 25/ Day 169 (pre-dose), Week 29/ Day 197 (pre-dose), Week 33/ Day 225 (pre-dose), Week 37/ Day 253 (pre-dose), Week 41/ Day 281 (pre-dose), Week 45/ Day 309 (pre-dose)

#### 48th dose:

Week 48/ Day 330 (pre-dose and 1 hour, 2 hours, 4 hours, 6 hours, and 8 hours post-dose), Week 48/ Day 331 (24 hours post-dose), Week 49/ Day 337 (7 days post-dose), Week 52/ Day 358 (4 weeks post-dose)

 Part 2-Extension and Part 2-Extension-2 (subjects participating from Part 2-Extension and Part 2-Extension-2)

#### First dose:

Week 1/ Day 1 (pre-dose and 0.5 hours, 1 hour, 2 hours, 4 hours, 6 hours, and 8 hours post-dose), Week 1/ Day 2 (24 hours post-dose)

#### Second dose:

Week 2/ Day 8 (pre-dose)

Fifth dose, ninth dose, 13th dose, 17th dose, 21st dose, 25th dose, 29th dose, 33rd dose, 37th dose, 41st dose, 45th dose:

Week 5/ Day 29 (pre-dose), Week 9/ Day 57 (pre-dose), Week 13/ Day 85 (pre-dose), Week 17/ Day 113 (pre-dose), Week 21/ Day 141 (pre-dose), Week 25/ Day 169 (pre-dose), Week 29/ Day 197 (pre-dose), Week 33/ Day 225 (pre-dose), Week 37/ Day 253 (pre-dose), Week 41/ Day 281 (pre-dose), Week 45/ Day 309 (pre-dose)

#### 48th dose:

Week 48/ Day 330 (pre-dose and 1 hour, 2 hours, 4 hours, 6 hours, and 8 hours post-dose), Week 48/ Day 331 (24 hours post-dose), Week 49/ Day 337 (7 days post-dose), Week 52/ Day 358 (4 weeks post-dose)

#### <Acceptable limits>

0.5 hours, 1 hour post-dose : ±5 minutes
 2 hours, 4 hours, 6 hours, 8 hours post-dose : ±10 minutes
 24 hours post-dose : ±1 hour
 72 hours post-dose : ±3 hours

#### <Rationale>

According to the result of a nonclinical study in which DS-5141b was administered to monkeys at 10 mg/kg, the Tmax of DS-5141b was  $4.00 \pm 2.00$  (mean  $\pm$  SD) and the terminal half-life, as a reference, was 296 hours. The terminal half-life of other AON was 29 days. Based on these pharmacokinetics results and with reference to "Clinical Pharmacokinetic Studies of Pharmaceuticals," one blood collection point directly before administration, at least 1 point before reaching the predicted Cmax, at least 2 points close to Tmax, and at least 3 points in elimination phase as the time points were selected since these were considered necessary forpharmacokinetic assessment.

# 6.8 Checking the DNA Sequence of the Site of DS-5141b Double-Strand Formation (Blood Collection [Whole Blood])

To check the DNA sequence of the site of DS-5141b double-strand formation in the dystrophin gene, after informed consent and before registration, 2 mL of blood will be collected in a blood collection tube prepared by the sponsor or central laboratory. After collection, the blood will be promptly mixed by inversion, and then transferred to a storage container prepared by the sponsor, and stored frozen (set temperature:  $\leq -20^{\circ}$ C) until it is submitted to the clinical specimen storage facility contracted by the sponsor. Details are specified in a separate procedure.

The investigator or subinvestigator will record whether blood was collected, the date of collection, and the result on the case report form.

# 6.9 Expression of Dystrophin Protein and Production of Exon 45-Skipped Dystrophin mRNA in Muscle Tissue (Muscle Biopsy)

To measure the dystrophin protein in muscle tissue and the dystrophin mRNA induced by exon 45 skipping, after registration, before the first dose of the study drug in each subject, after the last dose of the study drug (Day 85 to Day 99, or at withdrawal) in Part 2, after the last dose of the study drug (Week 49/ Day 337 to Week 51/ Day 351, or at withdrawal) in Part 2-Extension, and after the last dose of the study drug (Week 49/ Day 337 to Week 51/ Day 351, or at withdrawal) in Part 2-Extension-2, muscle tissue will be collected from, in principle, the biceps brachii muscle by open muscle biopsy. The location of collection will be decided after checking the condition of the muscle by MRI or CT performed in advance. After collection, the

specimen will be processed promptly, and stored frozen (set temperature:  $\leq -70^{\circ}$ C) in a container prepared by the sponsor or central laboratory until it is submitted to the clinical specimen storage facility contracted by the sponsor. Details are specified in a separate procedure.

The investigator or subinvestigator will record whether a muscle biopsy was performed, the date of biopsy, and the region of the collected muscle on the case report form.

#### 6.10 Measurement of Anti-Dystrophin Antibody (Blood Collection [Serum])

To measure anti-dystrophin antibody, 2.0 mL of blood will be collected in a blood collection tube prepared by the sponsor or central laboratory, before the first dose of the study drug and after the last dose of the study drug at each dose level (Day 15 or at withdrawal) in Part 1, before the first dose of the study drug and after the last dose of the study drug (Day 85 or at withdrawal) in Part 2, before the first dose of the study drug and after the last dose of the study drug (Week 49/ Day 337 or at withdrawal) in Part 2-Extension, and before the first dose of the study drug and after the last dose of the study drug (Week 49/ Day 337 or at withdrawal) in Part 2-Extension-2. After collection, the blood will be left for 30 minutes at room temperature and then centrifugal separation will be performed within 1 hour of collection, and the obtained serum will be divided into 3 storage containers. The obtained serum will be stored frozen (set temperature: ≤−70°C) until it is submitted to the clinical specimen storage facility contracted by the sponsor. Details are specified in a separate procedure. The investigator or subinvestigator will record whether blood was collected and the blood collection day on the case report form.

#### 6.11 Measurement of Anti-DS-5141b Antibody (Blood Collection [Plasma])

To measure anti-DS-5141b antibody, 1.0 mL of blood will be collected in a blood collection tube prepared by the sponsor or central laboratory, before the first dose of the study drug in Part 1 and after the last dose of the study drug at each dose level (Day 15 or at withdrawal) in Part 1, before the first dose of the study drug and after the last dose of the study drug (Day 85 or at withdrawal) in Part 2, after the last dose of the study drug (Week 49/ Day 337 or at withdrawal) in Part 2-Extension, and after the last dose of the study drug (Week 49/ Day 337 or at withdrawal) in Part 2-Extension-2. For subjects participating from Part 2-Extension, blood will also be collected before the first dose of the study drug in Part 2-Extension, and for subjects participating from

Part 2-Extension-2, blood will also be collected before the first dose of the study drug in Part 2-Extension-2. After blood is collected, inversion mixing will promptly be performed and it will be cooled with ice. The plasma obtained from centrifugal separation will be stored frozen (set temperature: ≤−70°C) until it is submitted to the clinical specimen storage facility contracted by the sponsor. Details are specified in a separate procedure.

If anti-DS-5141b antibody is positive in the follow-up period (or at withdrawal), additional blood will be collected to investigate anti-DS-5141b antibody. Additional blood collection will be performed until the anti-DS-5141b antibody titer is found to have decreased below baseline (if anti-DS-5141b antibody was found at baseline), until the subject entered in a new study, or until the subject withdraws consent, whichever is earliest. The investigator or subinvestigator will record whether blood was collected and the date of blood collection on the case report form.

#### 6.12 Exploratory Biomarker Research

# 6.12.1 Imaging Analysis of skeletal muscle

To examine the disease progression and fat replacement in skeletal muscle, MRI will be performed in the thigh before the first dose of the study drug in each subject, before the first dose of the study drug (Day 85 to Day 99, or at withdrawal) in Part 2, before the first dose of the study drug in Part 2-Extension, and before the first dose of the study drug and after the last dose of the study drug (Week 49/ Day 337 to Week 51/ Day 351, or at withdrawal) in Part 2-Extension-2, and the data will be submitted to the sponsor. Details of procedures and the data analysis facility will be specified separately. This exploratory biomarker research will only be performed for subjects in whom MRI can be performed appropriately.

The investigator or subinvestigator will record whether MRI was performed, the date of imaging, and the location of imaging on the case report form.

